### **Data analysis**

Preparation for decision making mean scores will be compared post-intervention at each time point across the two groups using Student's T-test. Associations between participant preparation scores, their level of domain specific knowledge, and socio-demographics will be explored using regression analyses. The primary analysis

will be focused on the pregnant women (or minors), with secondary analyses comparing between partners, and partners and women (or minors) within couples using paired T-tests.

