Partnership and Advocacy		
1. Because of the app, did you ask more questions at your doctor visits?		43
2. Because of the app, did you and your partner discuss pregnancy or prematurity issues?		86
3. Did you share information given in the app with other family/friends (excluding a partner already enrolled in the study)?		57

**Theoretical frameworks and hypotheses.** Cognitive load theory suggests that an individual's capacity to process information is finite and limited by the individual's initial processor of information referred to as "working memory." The Dual Code Theory suggests that humans have separate working memory for auditory/text information and for visual information. Using both routes increases uptake of information. The Theory of Multimedia Learning states that even when cognitive load is not an issue, people will learn more with a blend of combined media than from a single medium. Finally, according to the Health Belief Model, health behavior (decisions) stem from beliefs (knowledge), perceived benefits of and barriers to action, and self-efficacy.

Thus, **we hypothesize** that the multimedia P3 mobile education will result in 1) higher parental knowledge and 2) better preparation for decision making compared to a static, electronic ACOG educational handout.

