#### Randomization

**1)** Pregnant women (or minors) who consent to participate will be randomized 1:1 to the P3 mobile education (intervention) or the link to electronic ACOG handout arm (active control), with assignment to be determined by REDCap displaying the computer-generated random assignment. Block randomization will be used with random block sizes of 2 and 4, based on the gestational age of the pregnant woman at the time of enrollment, with participants with baseline assessment during weeks 16-18 in one block, and those with baseline during weeks 19-21 in another block. A randomization list will be generated using the R package *blockrand*

**2)** Eligible partners who consent to participate will be assigned to the same intervention group as the pregnant participant, otherwise they will contaminate each other.

**3)** Participants will receive either links to ACOG education or be added as a user to the P3 mobile education site via email or text to their smartphone. The CRA will then provide a brief tutorial and the study team contact information.

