##### Data collection. (Please see Survey Schedule in Section 52.)

At baseline (16-21 weeks) the CRA will administer the *health literacy assessment*, will ask participants to self-administer the *Entry Questionnaire*, an *anxiety measure*, and a subjective *global health measure*, and will abstract *maternal clinical data* and *reproductive history* from the medical record.

As pregnancy continues, REDCap will automatically send out questionnaires to participants at key time points: the start of their 25th, 30th, and 34th weeks. These times will include *Prematurity Knowledge Questionnaires* (specific to their gestational age), a *Preparation for Decision Making scale*, and an *anxiety measure*. At these time points, if they do not complete the questionnaire the first day they are sent it, they will

be sent an automatic reminder through REDCap for the next 2 days. If the participant still has not completed the questionnaire by this time, the CRA will contact the participant by phone.

At study completion, within two weeks of either preterm childbirth or completion of the 34 week questionnaire, participants will be asked to also complete the *Educational-Aid Questionnaire*.

Participants will receive \$20 for each completed follow-up assessment (up to \$80) and entered into a lottery to win an additional \$50 for every questionnaire they return the day they were sent it.

Data will be collected and managed using the REDCap (Research Electronic Data Capture) system. This system is a secure, web-based application designed to support data collection for research. It provides data validation, audit trails, and automated export procedures to statistical packages. Branching logic and calculated fields can also be created in the system to support data entry.

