## **Sample Size**

Based on our published data for knowledge of long-term outcomes, we expect average parent knowledge of seven long-term outcomes of 50% (SD 35%) in the ACOG group. In our population, English literacy is ~90% while ~80% possess smartphones. With 50 participants in each group, we can detect a 20% difference in knowledge, with power of 80% and  $\alpha$  of 0.05. To allow for 10% attrition, 55 pregnant participants will be enrolled in each group.

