### **Data Analysis**

[name] will perform 1) blinded scoring of the Prematurity Knowledge Questionnaire using prespecified rules for each response, and 2) blinded analysis with masked group assignment in the dataset. The randomized design, the blinded scoring, and the blinded comparison of post-intervention NICHD recommended knowledge between the P3 and ACOG groups should achieve robust and unbiased results. The Educational-Aid Questionnaire responses and the P3 tracking data will be analyzed separately after completion of the other analyses.

Statistical analyses will be conducted in SAS. The primary outcome is the knowledge score for long-term outcomes (cerebral palsy, learning problems, behavior problems, chronic lung disease, blindness, and hearing impairment), and the primary analysis will use Student's t-test to compare the two groups on knowledge of long-term outcomes at 25 weeks. We will use regression methods to examine relationships between knowledge and sociodemographic characteristics, health literacy level, and the mobile intervention use pattern captured by the P3 software. Additional planned analyses will compare knowledge at later time points and in the other NICHD-recommended domains, e.g. short-term outcomes, as well as differences between groups in preparation for decision-making scores and anxiety scores. We will also use regression methods to examine relationships between knowledge and sociodemographic characteristics, health literacy level, and the mobile intervention use pattern captured by the P3 software.

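### Aim 2 tests preparation for decision making at three weeks with no principal week or multiplicity rule, and its t-test leaves out the randomisation stratum

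*Combined protocol and SAP*

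**What the plan says.** The hypotheses paragraph that closes the Background sets two expectations for P3 side by side: higher knowledge and "better preparation for decision making compared to a static, electronic ACOG educational handout". The second has its own aim, sample-size paragraph and analysis section.

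The Aim 2 Data analysis section states: "Preparation for decision making mean scores will be compared post-intervention at each time point across the two groups using Student's T-test". The weeks come from the Aim 1 Data collection section: "As pregnancy continues, REDCap will automatically send out questionnaires to participants at key time points: the start of their 25th, 30th, and 34th weeks". The Aim 2 section does use the term primary analysis, but there it selects a population (pregnant women or minors) and not a week.

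Aim 1 is specific: "the primary analysis will use Student's t-test to compare the two groups on knowledge of long-term outcomes at 25 weeks". The same section places the Aim 2 outcome among additional planned analyses, "as well as differences between groups in preparation for decision-making scores and anxiety scores", with no week and no error-rate rule.

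The Aim 2 Sample size section gives 80% power for 0.6 points (SD 1.0) with 100 analysed, and names no week.

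The Randomization section says that blocks are formed "based on the gestational age of the pregnant woman at the time of enrollment", with weeks 16-18 and weeks 19-21 kept apart. The Aim 2 test has no term for this.

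**The concern.** Hypothesis 2 is one claim, but the plan will produce three p-values for it. The plan does not say whether one significant week is enough, whether all three are needed, or whether each week answers a separate question. The claim could therefore be settled after the results are seen, by picking the week that came out best. At stake is how far the Aim 2 conclusion can be trusted; the dissemination section plans manuscripts corresponding to Aims 1 and 2.

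There is also a smaller point. Randomisation within gestational-age strata balances the arms on that factor. An unadjusted t-test leaves between-stratum variation in its error term, so it is slightly too cautious and gives up a little power.

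**Working it through.** **Inputs.** Three tests (weeks 25, 30, 34), 1:1 allocation, 100 analysed (50 per arm), difference 0.6 and SD 1.0 come from the plan. Aim 2 states no alpha or sidedness, so two-sided 0.05 is assumed, with alpha taken from Aim 1. Between-visit correlations and the share of variance explained by the stratum are not in the documents, so ranges are assumed.

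**1. The plan's own power figure.** Noncentrality = 0.6 / (1.0 × √(2/50)) = 0.6 / 0.2 = 3.0. With 98 degrees of freedom this gives power of 84.4%. Solved the other way, 80% power at 50 per arm detects 0.57 points, which rounds to the stated 0.6. The 80% is therefore a rounded, conservative figure.

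For later weeks, the Aim 1 Sample Size section says: "To allow for 10% attrition, 55 pregnant participants will be enrolled in each group". Power is 80.4% at 45 per arm and 79.5% at 44. Relative to 55 enrolled, 45 is a loss of 1 − 45/55 = 18.2%. Follow-up can end early, since study completion falls "within two weeks of either preterm childbirth or completion of the 34 week questionnaire", but the documents do not show a loss of that size.

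**2. At least one false positive in three tests, either direction.** Independent: 1 − 0.95³ = 14.3%. With equal correlation r between the test statistics and c = 1.96, the chance is 1 − ∫ φ(x) [Φ((c − √r·x)/√(1−r)) − Φ((−c − √r·x)/√(1−r))]³ dx.

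**3. Only results favouring P3.** Hypothesis 2 has a direction. Independent: 1 − 0.975³ = 7.3%. With correlation, drop the second Φ term from the integral. The comparator for one two-sided 0.05 test is 2.5%.

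| Assumed r | Either direction | Favouring P3 |
|---|---|---|
| 0 | 14.3% | 7.3% |
| 0.5 | 12.5% | 6.3% |
| 0.7 | 10.9% | 5.5% |
| 0.9 | 8.4% | 4.2% |
| single test | 5.0% | 2.5% |

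**4. Two ways to control the error.** One named week at two-sided 0.05 keeps 84% power at 50 per arm. Bonferroni over three weeks uses 0.05/3 = 0.0167 per test. That gives 71% power at 50 per arm and needs 59.6, so 60, analysed per arm for 80%; the plan enrols 55.

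**5. Ignoring the stratum.** Take two equal strata balanced by arm, explaining a share R² of the score variance. The true variance of the arm difference is (1 − R²) times what the t-test assumes, so its actual error rate is about 2[1 − Φ(1.96/√(1 − R²))]. This gives 4.8%, 4.4% and 3.9% at R² of 2%, 5% and 10%. Simulation (100,000 trials per setting, 50 per arm) agrees to within about 0.1 points, and the model with arm and stratum holds about 5%. For 0.6 points, that model adds about 0.4 to 0.5, 1.1 and 2.3 to 2.4 points of power respectively.

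**The case against.** The strongest reply is that this is not the primary outcome. The plan fixes one primary outcome, test and week, and lists preparation scores as additional. That stands, and it limits the weight of the point. It does not remove the gap, because a hypothesis with its own power statement needs a rule for what would count as support.

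A second reply is that no section says one significant week suffices, so the inflated rates describe a reading that the plan never adopts. That is correct: the rates are conditional on that reading. But nothing rules it out.

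A third is that the three weeks may ask different questions. The Aim 2 Study measures section says the scale is tailored to decisions about resuscitation, hospital choice and breastfeeding at suitable time points. A reader might infer one decision per week. The documents do not give such a mapping, so neither the claim that the choice of week settles which decision is meant, nor the defence that there are three separate questions, can be established.

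A reader might also infer that the chance of wrongly supporting hypothesis 2 always exceeds 5%. Counting only results favouring P3, it is 4.2% at a correlation of 0.9. The fair comparison is with 2.5%, and inflation remains on that basis.

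Finally, the stratum has nothing to do with multiplicity, and the unadjusted t-test is valid. Both are true. Adjustment is a small gain at almost no cost.

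**Conclusion.** The point holds for an additional outcome. Aim 2 has three unadjusted tests of one hypothesis and no stated way to read them together. If any one significant week were taken as support, the false-positive chance would be about 8% to 14% in either direction, or about 4% to 7% in favour of P3, against 5% and 2.5% for a single test. These figures assume two-sided 0.05 and equal correlations between 0 and 0.9.

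Two stronger readings are not supported. The trial's primary result is not compromised, because the 25-week knowledge test stands alone. The 80% power figure is not an error either: power is 84% at the planned 50 per arm, and no shortfall at later weeks is documented. That the power statement names no week is only a gap in wording.

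Omitting the stratum is minor. At an assumed 2% to 10% of variance explained, the t-test runs at about 4.8% to 3.9% in place of 5%.

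**What to change.** If the arms have not yet been compared:

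- Name one week as the single Aim 2 test in pregnant participants, at two-sided 0.05. Week 25 is suggested because it matches the Aim 1 time point and is the follow-up least affected by delivery. Tie the 80% power statement to that week. The authors may prefer another week; what matters is that it is fixed in advance.
- Report the other weeks as estimates with 95% confidence intervals and numbers per arm, without a confirmatory claim.
- Compare arms with a linear model containing arm and the gestational-age stratum as recorded at randomisation. Use the recorded value, because the strata are described for weeks 16-21 while the inclusion criteria admit from week 14.

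The cost is SAP wording and one model term, with no new data or participants. The downside is that no confirmatory claim can be made at 30 or 34 weeks. The documents do not show whether the arms have already been compared. If they have, a week named now would be post hoc and should be labelled so, with all three weeks reported.

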#### *Addressing Missing Data.*

Despite our best efforts to prevent study dropout and missing data, we anticipate there will be some study dropout. If one member of a couple decides to drop out, we will try to retain the other member. We will attempt to describe differences among those who do and do not drop out, with the goal of characterizing the uncertainty created by missing data. We will explore whether certain characteristics are more prevalent among participants who drop out, e.g., high anxiety or neonatal death.

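### The 25-week primary t-test can use only women with a score, dropouts are merely described, and no planned analysis shows whether a borderline result survives the missing data

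*Combined protocol and SAP*

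**What the plan says.** The Data Analysis section under Aim 1 sets the endpoint, "The primary outcome is the knowledge score for long-term outcomes", and the test: "the primary analysis will use Student's t-test to compare the two groups on knowledge of long-term outcomes at 25 weeks". It names no analysis set, no imputation and no likelihood-based model. It expects randomisation and blinded scoring to keep the comparison free of bias.

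The Addressing Missing Data section foresees some dropout and says the team will try to keep the other member of a couple. It then states its method: "We will attempt to describe differences among those who do and do not drop out". The purpose given is to convey how uncertain the results become when data are missing. It will also look at whether some traits are commoner among "participants who drop out, e.g., high anxiety or neonatal death".

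Elsewhere, attrition is met by enrolling more women: "To allow for 10% attrition, 55 pregnant participants will be enrolled in each group". The Data collection section adds automatic reminders, a phone call and payment for each follow-up. The only sensitivity analysis in the plan, under Potential Challenges and Alternative Strategies, compares questionnaires answered in person with those answered at home. It does not address missing scores.

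**The concern.** A t-test without imputation drops every woman who has no 25-week score. That the analysis is therefore one of completers is an inference, since the plan does not use the word, but it is a fair one. Such an estimate is unbiased for the randomised women only if, within each arm, those missing resemble those observed. Randomisation and blinded scoring do not secure this.

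The documents give some reason to think that dropout could differ by arm. Under Study Groups, only P3 women receive up to two text messages a day, with possible reminders; control women receive links. In the P3 pilot reported in the Background, 14% said the app raised their anxiety unnecessarily and 21% reported more anxiety as time passed. Use ranged from 6 minutes to 14 hours per participant. If less engaged and less knowledgeable women were lost from P3 alone, the observed difference would be too large.

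A table comparing dropouts with completers would not show this. It neither changes the estimate nor says how different the missing women would have to be to change the conclusion.

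**Working it through.** **Inputs.** From Sample Size (Aim 1): ACOG mean 50%, SD 35%, difference 20 points, 50 analysed and 55 enrolled per group, 10% attrition, alpha 0.05. Sidedness is not stated.

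**The plan's own figure.** Two-sided, SD 35, difference 20: the normal approximation gives 49 per group and the exact noncentral t gives 50, with power 80.8% at 50. A one-sided test would need only 38, so the plan's figure is two-sided. Inflating for 10% attrition, 49/0.9 gives 55 and 50/0.9 gives 56. The stated 50 and 55 are reproduced.

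**Tipping-point calculation.** Assumptions that are not in the documents: missing ACOG women score like ACOG completers, missing P3 women score lower than P3 completers by a shortfall d, and the standard error stays at the completers' value.

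- SE = 35 × √(2/n), with n observed per arm; threshold C = t(0.975, 2n − 2) × SE.
- Adjusted difference = D − f × d, where D is the observed difference and f the share missing in P3.
- Significance is lost once d exceeds (D − C)/f.

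*About 10% missing per arm, taken two ways.*

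- 5 of 55 missing: n = 50, SE = 7.0, C = 13.89, f = 5/55.
- Exactly 10%: n = 49.5, SE = 7.03, C = 14.0, f = 0.1.

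*20% missing per arm* (11 of 55): n = 44, SE = 7.46, C = 14.83, f = 0.2.

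| Observed D | 5 of 55 missing | exactly 10% | 20% missing |
|---|---|---|---|
| 14 | (14 − 13.89) × 11 = 1.2 | 0 | not significant |
| 16 | (16 − 13.89) × 11 = 23.2 | 20 | (16 − 14.83)/0.2 = 5.8 |
| 18 | 45.2 | 40 | 15.8 |
| 20 | 67.2 | (20 − 14.0)/0.1 = 60 | (20 − 14.83)/0.2 = 25.8 |

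*All 10 missing women in P3, none in ACOG.* SE = 35 × √(1/45 + 1/55) = 7.03, C = 13.96, f = 10/55. The tipping shortfall is 11.2 at D = 16 and 33.2 at D = 20.

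**A milder case: missing P3 women score at the ACOG mean** (5 of 55 missing per arm, SE 7.0). The difference becomes D × 50/55:

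- D = 14 becomes 12.7, p = 0.072.
- D = 16 becomes 14.5, p = 0.040.
- D = 20 becomes 18.2, p = 0.011.

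Only observed differences between 13.9 and 13.89 × 55/50 = 15.3 lose significance.

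**How likely is a borderline result?** If the true difference among completers is 20 with SE 7.0, the normal chance of observing 13.9 to 16 is Φ(−0.57) − Φ(−0.87), about 9%. For 13.9 to 18 it is Φ(−0.29) − Φ(−0.87), about 20%.

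**The case against.** The strongest reply is that the design is robust where it was meant to be. At the planned 20-point effect and 10% attrition, missing P3 women would have to score 60 to 67 points below P3 completers. With completers at 70%, that means about 3% to 10%. Even an observed 16 points stays significant if the missing P3 women gained nothing. The 10% shortfalls that overturn 16 or 18 points exceed the benefit itself, so the missing women would have to know less than controls. Similar shortfalls in both arms would largely cancel. All of this stands.

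Ignoring the video texts is also not the same as missing the questionnaire. The questionnaire is sent separately through REDCap, with reminders, a phone call and payment, and collection at prenatal visits is also planned. A woman who skips the videos but answers stays in the analysis. Differential dropout is therefore possible but not shown.

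A reader might infer that the plan expects dropout driven by anxiety and neonatal death. It does not: both are examples of traits to be explored. Neonatal death could remove a 25-week score only after a birth before that assessment, so most such losses would affect the 30- and 34-week data.

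Finally, imputation has limits here. No knowledge score is listed at baseline, women who leave before 25 weeks have no later scores, and the later questionnaires are tailored to gestational age. This argues for putting weight on the tipping-point analysis. It does not argue for having no analysis.

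**Conclusion.** The concern holds as a cheap improvement. The stated method, describing dropouts, cannot meet the section's own aim, and no other planned analysis does so. The plan also does not say how a birth before the 25-week assessment enters the primary comparison.

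The size depends on the result. With about 10% missing per arm, an observed 20 points is safe, an observed 16 is overturned by a shortfall of about 20 to 23 points, and an observed 14 by about 0 to 1. At 20% missing, the shortfalls are about 6 at an observed 16 and 26 at an observed 20. These figures rest on SD 35, missing ACOG women like ACOG completers, and an unchanged standard error. The 20% and P3-only scenarios are assumptions beyond the plan.

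A reader might go further and conclude that the primary result is fragile or biased. The documents do not support that: at the planned effect and attrition it is robust, and nothing shows that missingness will differ by arm. What is missing is a planned check for the borderline case.

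**What to change.** Keep Student's t-test as the primary analysis. In Data Analysis and Addressing Missing Data, add:

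1. A table of missing 25-week scores by arm.
2. A statement of how births before the 25-week assessment are handled, both in the primary comparison and in any imputation.
3. Two pre-specified sensitivity analyses in randomised pregnant participants:
   - Multiple imputation by arm from baseline data already collected: gestational-age stratum, health literacy, anxiety, global health and socio-demographics. Use later knowledge scores only where a woman missed 25 weeks but answered later and the items are comparable.
   - A delta-adjusted tipping-point analysis that lowers imputed P3 scores in steps until significance is lost, with the tipping value reported beside the primary result.

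The cost is about a paragraph in the plan and a little more analysis work, with no new data collection. The downside is that a borderline finding may be shown to be fragile.
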